Together, these data support our *overarching hypothesis*: that with the same volume of exercise, **HIIT will lead to better physical function and reduced patient-reported fatigue through improvements in mitochondrial bioenergetics compared with CME among older PWH**. We further hypothesize that older PWH randomized to HIIT will maintain self-directed exercise better than those in CME when exercise is no longer supervised, and that behavioral support will help to maintain adherence. Through a three-site (Seattle, WA, Aurora, CO, and Birmingham, AL), clinical trial comparing the clinical and bioenergetic effects of two exercise regimens that vary by interval and intensity (HIIT or CME), we will test our hypotheses through the following aims:

**AIM 1.** Compare the effects of two exercise regimens varying by interval and intensity on *primarily* physical function performance (i.e., 400-m walk time) and *secondarily* on patient-reported fatigue at 16-weeks. We **hypothesize** that PWH randomized to HIIT will experience greater improvements in physical function and reductions in fatigue compared

to CME. **Approach:** We will randomize 180 PWH (aged 50-80 years) into one of two supervised 16-week exercise interventions and compare changes in physical function and patient-reported fatigue over time.

**AIM 2.** Evaluate bioenergetic mechanisms underlying HIIT and CME. We **hypothesize** that PWH randomized to HIIT will have improved mitochondrial bioenergetics (i.e., mitochondrial respiration rate and ETC activity). **Approach:** We will evaluate 16-week changes in skeletal muscle and systemic (peripheral blood mononuclear cells [PBMCs]) mitochondrial activity among PWH in response to supervised exercise.

**AIM 3.** Describe and compare the effect of a biobehavioral coaching intervention to enhance self-directed exercise. **Approach:** After 16 weeks of supervised exercise, HIIT and CME participants will be randomized (in a factorial design) to a 12-week coaching intervention (vs. control) using tailored text messages to support exercise adherence. Physical activity amount (via accelerometry) and experience (via interviews) will be compared between arms using mixed analytic methods.

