#### Exploratory Outcome Measures

1. Change in 1-RM adjusted for lean body mass from week 0-16.
2. Change in VO2 maximum from week 0-16.
3. Change in Short Performance Physical Battery (SPPB) and modified SPPB from week 0-16 and 0-28

4. Change in PROMIS-measured fatigue from week 0-16 and 0-28.
5. Change in DXA-measured total body fat and lean body mass from week 0-16.
6. Change in electron transport chain activity (skeletal muscle) from week 0-16.
7. Change in electron transport chain activity (PBMCs) from week 0-16.
8. Change in mitochondrial content (skeletal muscle) from week 0-16.
9. Change in mitochondrial content (PBMC) from week 0-16.
10. Change in physical function outcomes, patient-fatigue and physical activity adherence from week 17-28 by exercise and coaching intervention.
11. Change in mitochondrial bioenergetics, physical function and fatigue at baseline, week 16, and change from 0-16
12. Change in self-reported 3 day diet intake from week 0-16.
13. Change in stool microbiome and short-chain fatty acids from week 0-16
14. Change in muscle fat by proton density fat fraction (PDFF), intramyocellular lipid (IMCL) and extramyocellular lipid (EMCL) from week 0-16
15. Change in oxidative phosphorylation (OxPhos) from week 0-16.
16. Change in mean VO2 response *in the gastrocnemius and soleus muscles* from week 0-16.
17. Change in lean muscle quality and quantity from week 0-16 by muscle ultrasound.
18. Explore the barriers and facilitators for non-participation in an exercise-related clinical trial.
19. Change in cognitive functioning (i.e., global and domain T scores) and subjective cognitive symptoms (self-report questionnaires) from 0 to 48 weeks.
20. Change in blood markers (neurotrophins [e.g., BDNF], growth factors [e.g., VEGF], pro-inflammatory cytokines [e.g., IL-6]) from 0 to 48 weeks
21. Change in neuroimaging markers: cerebral blood flow, resting state functional connectivity, and brain volume), from 0 to 16 weeks (UAB SITE ONLY)
22. Psychological mechanisms of adherence to exercise at 48 weeks (measured with questionnaires and text message surveys)

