**B. Description of Population to be Enrolled:**

|            | Consented | Begin Intervention | Number of women | Complete Intervention |
|------------|-----------|--------------------|-----------------|-----------------------|
| Colorado   | Up to 100 | N=60               | Goal 25%        | N=50                  |
| Seattle/UW | Up to 100 | N=60               | Goal 25%        | N=50                  |
| UAB        | Up to 100 | N=60               | Goal 25%        | N=50                  |

This study will involve the recruitment and retention of men and women ( $n=180$ ) at three sites ( $n=60$  each site) with HIV infection who are stable on HIV antiretroviral therapy. Study volunteers must meet general criteria to be eligible for further screening for participation in the study. In most cases, this information will be acquired during a telephone interview prior to a screening/consent visit. *The inclusion and exclusion criteria have been carefully selected to enroll the most appropriate study population while also protecting the generalizability of the findings.* All participants will engage in a 16-week randomized exercise intervention (high-intensity interval training [HIIT] vs continuous moderate exercise [CME], followed by a 12-week exercise maintenance intervention in which participants are also randomized to a coaching vs control intervention. Up to 40 participants will be given the opportunity to co-enroll in a qualitative substudy (Aim 3) where they will participate in three one-on-one interviews (at weeks 0,16,28) to capture perspectives on sustaining a self-directed exercise habit. Up to 40 participants (Colorado and Washinton only) will be given the opportunity to participate in an MRI/MRS substudy with imaging at baseline and week 16. Up to 20 participants (Colorado, Washinton, and Alabama) will be given the opportunity to complete the 16 week exercise intervention at a recreational center. The total study duration will be 28 weeks at UCD and UW with the option to enroll in a 12 month follow up (48 weeks). The total study duration will be 48 weeks at UAB.

**Characteristics of the Population:** Potential participants will be recruited from HIV specialty clinics at our sites. Adults living with HIV will be included if they meet the following eligibility criteria:

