*Baseline visit #3. Physical function and (optional) muscle ultrasound.* The **primary physical function outcome will be 400-MWT**, a well-established measure shown to better discriminate early physical function decline among higher functioning adults, and is a reliable outcome in clinical trials, including the LIFE Trial. The Short Performance Physical Battery (SPPB) and a modified version (mSPPB) will be obtained. The SPPB is an objective assessment of physical function associated with short-term mortality, disability, and hospitalizations. The mSPPB improves discrimination of physical function by increasing repeat chair stands from 5 to 10, standing balance test for 30 seconds instead of 10, and adding a single leg stand. Physical function will be measured every 4 weeks by a research assistant blinded to intervention arm. The 400-MWT, SPPB, and mSPPB will be administered at both sites using standard scripts. Additional measures of frailty will include self-reported fatigue, weight loss, and exhaustion, and objective measures of grip strength by hand held dynamometer. The 400-MWT and the 10x chair stands from the mSPPB will be done every 4 weeks; the full physical function battery will be completed at baseline, week 16, and week 28. For the optional muscle ultrasound, we will collect sonographic images to provide estimates on lean muscle mass (aggregate muscle thickness, cm) and myosteatosis (grayscale values) using the Phillips Lumify L 12-4 linear array transducer. Sonographic estimates of lean muscle mass will be taken at the midpoint of the upper trapezius, pectoralis major, lateral deltoid, brachioradialis, rectus femoris, and tibialis anterior while the participant lays supine for 15-20 minutes.

*Baseline visit #4: MRI/MRS.* Prior to the initiation of exercise training, participants will undergo baseline MRI/MRS studies as detailed below. All of the proposed imaging modalities in the ancillary HEALTH+ Study Aims 1-3 can be completed within one-hour in the research scanner, located in the building adjacent to the Exercise Research Laboratory at UCD-AMC and the 14T MR Lab and [name] laboratory facilities at UW. Participants will be instructed to avoid vigorous activity for 2 days prior to the imaging studies. The imaging will be repeated during weeks 16, or within 4 weeks of the final exercise visit for PWH in the HEALTH study.

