#### **Procedures/Outcome Measures:**

**Randomization.** After the conclusion of the exercise intervention, participants will be randomized 1:1 (with even allocation of HIIT vs CME) to receive the coaching or control intervention (details below).

**Quantitative Measures.** PA will be measured with a widely-used and validated measure, the ActiGraph accelerometer (ActiGraph, LLC, Fort Walton Beach, FL), as described in Aim 1. **Primary exercise endpoints** are (1) time spent in moderate-to-vigorous PA (MVPA), and (2) steps per day.

These endpoints will be set with the adult cut-points for tri-axial accelerometers. All participants will complete a daily log during the maintenance phase to track aerobic and resistance exercise. This log will include the time, type, duration, and setting of exercise completed each day. It will be triangulated with the accelerometry data and reported descriptively.

**Qualitative Measures.** **One-on-one Interviews (this will be optional).** First, we will pilot test an interview guide on 2-3 PWH at UW and UCD-AMC and revise it accordingly. A final guide will be used to direct subsequent interviews consistently at both sites. The interviews will take place in a secure, private location. Questions will address the participants' perceptions of exercise; experiences with HIIT, CME, or resistance training; the coaching intervention; and what they think will help them sustain PA over the long-term (Fig. 4). If a participant withdraws from the study, he/she may be offered a withdrawal interview to explore reasons for withdrawal and/or ways to improve the study intervention. Interviews will take ~ 30 minutes, be audio-recorded, and transcribed verbatim. [name] has over 15 years of experience designing, implementing, and analyzing data from qualitative studies and has successfully trained and managed qualitative data collectors across sites, obtaining high-quality data.

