#### D. Description, Risks and Justification of Procedures and Data Collection Tools:

**Muscle biopsy.** Participants agreeing to muscle biopsy will have a biopsy prior to and at the completion of the 16 week intervention. Participants will be advised to refrain from any physical activity for at least 48 hours following the biopsy. Non-steroidal anti-inflammatories or aspirin are held for 7 days prior to the biopsy. If participants are taking direct oral

anticoagulants, this will be held for 48 hours prior to the procedure (72 hours if creatinine clearance is 30-50 and taking dabigatran) if approved by their primary provider. Therapy can be resumed 24 hours after the procedure, or as instructed by their physician. At study completion, subjects will be asked to return within 10 days of the final exercise session for a muscle biopsy. The exercise intervention will begin >48 hours after the initial biopsy, but within 28 days. Participants will be asked to abstain from alcohol or caffeinated beverages after 1300h and to fast from any food or drink beginning at 9pm with the exception of water. The biopsy will be completed prior to 10am local time. Percutaneous samples of the vastus lateralis muscle will be obtained. After cleansing the area of the thigh with antiseptic (e.g., chlorhexidine, Betadine solution), 1% lidocaine (without epinephrine) will be injected under the skin. A 3-5 mm incision will be made in the skin and fascia over the belly of the vastus lateralis, and 100-150 mg of muscle tissue will be removed using a Bergstrom side-cutting biopsy needle with suction applied. The incision will be closed and a compression wrap and ice will be applied to the incision area for 30-45 minutes. The patient will be given instructions for wound care before discharge.

**Risks:** The risks associated with muscle biopsy include brief, mild burning pain from the local anesthetic (lidocaine), more than mild discomfort during the acquisition of tissue (about 10% of cases), and infection (less than 0.4% of cases). Allergy to the anesthetic (skin swelling or rash) occurs rarely. There may be persistent numbness in the biopsy area.

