## F. Data Analysis Plan:

**Statistical Considerations.** We hypothesize that among older PWH, HIIT will lead to better physical function and reduced fatigue through improvements in mitochondrial bioenergetics compared with CME.

**Sample Size Calculations:** We assume a 1:1 randomization to HIIT or CME balanced by site, sex ( $\geq 25\%$  women) and age category (50-59, 60-69, and 70+) with a conservative 20% dropout rate, resulting in 40 evaluable participants/group. The second randomization at week 16 and will also be balanced by initial randomization (2x2 factorial design). Aim 1 and 2 power calculations assume two-sided, 2-sample/paired *t*-tests for between/within group comparisons of the change from baseline with a 0.05 significance level. We assume conservative within subject correlations ( $\rho$ ) of 0.7 or 0.5 to estimate the standard deviation (SD) of the outcome change, larger correlations and repeated measures will result in additional power. The Aim 1 primary outcome is change in 400-MWT. We assume an effect size comparable to Toohey, an intervention comparing HIIT to CME among middle-aged (mean age 51, SD 12 years) cancer survivors that resulted in a mean (SD) difference of 97 (82) and 36 (68) meters in 6-minute walk distance among HIIT and CME, respectively. Using  $\rho=0.7$ , and a sample size of 40/group, we will have  $>88\%$  power to detect a comparable *between* group differences of 45 (38) and 20 (38) second improvement in 400-MWT in HIIT and CME, respectively. For reference, in our prior exercise study, PWH had a 25 second improvement in 400-MWT. This also provides  $>99\%$  and  $>81\%$  power to detect *within* group differences in the HIIT and CME arms. For morning and evening fatigue, we assume a baseline mean of 19(8) and 27(8) points, respectively ([name], unpublished data). With  $\rho=0.5$ , and a sample size of 40/group, we will have  $>80\%$  to detect a change of  $\geq 27\%$  and  $\geq 20\%$ , respectively. The primary Aim 2 outcome is change in State 3 respiration. Based on Robinson, we estimate a baseline mean (SD) of 580 (180) pmol  $O_2$ /min/mL using  $\rho=0.5$ . This provides  $>81\%$  power to detect a difference in the change of 50% (HIIT) and 30% (CME). The muscle substudy is considered exploratory, however, we anticipate adequate power. Using preliminary data, combining HEALTH+ exercise groups (N=24), provides  $>80\%$  power to detect a change of -8.7% in MRI-PDFF of HEALTH+ participants. For within exercise group (CME or HIIT) comparisons, a sample size of 12 provides  $>80\%$  power to detect a difference of -12.5%. For the CME versus HIIT change from baseline comparison, a sample size of 12 per group provides  $>80\%$  power to detect group differences of 9.8%. For the change in OxPhos, combining HEALTH+ exercise groups (N=24, 3 dropouts/group), provides  $>80\%$  power to detect an OxPhos change of 0.039. For within exercise group (CME or HIIT) comparisons, a sample size of 12 provides  $>80\%$  power to detect an OxPhos difference of 0.055. For the CME versus HIIT change from baseline comparison, a sample size of 12 per group provides  $>80\%$  power to detect group OxPhos differences of 0.056. For the change in aim 3, combining HEALTH+ exercise groups, a sample size of N=24 (3 dropouts/ group), provides  $>80\%$  power to detect a 21%  $\dot{V}O_2$  change in HEALTH+ participants. For within exercise group (CME or HIIT) comparisons, a sample size of 12 provides  $>80\%$  power to detect 33% change in  $\dot{V}O_2$ . For the CME versus HIIT change from baseline comparison, a sample size of 12 per group provides  $>80\%$  power to detect a 30% difference in the 16-week change from baseline.

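### The week-16 muscle MRI/MRS may be taken up to 4 weeks after supervised exercise ends, with no rule placing it before the second randomisation, yet it is analysed as change over 16 weeks of training

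*Combined protocol and SAP*

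**What the plan says.** **Scan.** Section IV.C, Baseline visit #4: "The imaging will be repeated during weeks 16, or within 4 weeks of the final exercise visit for PWH in the HEALTH study".

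**Biopsy.** Section IV.D, Muscle biopsy: "subjects will be asked to return within 10 days of the final exercise session for a muscle biopsy". This is worded as a request, and the biopsy is optional (Baseline visit #2).

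**Second randomisation.** Aim 3, Randomization: "After the conclusion of the exercise intervention, participants will be randomized 1:1". The sample size paragraph of section F dates it to week 16 and balances it by exercise arm. Section IV.B describes the supervised phase as "followed by a 12-week exercise maintenance intervention in which participants are also randomized to a coaching vs control intervention", so maintenance runs from week 17 to week 28.

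**Schedule.** As far as the column positions can be read, Table 3 puts the repeat MRI, the biopsy and the second randomisation in one End of Part 1 column, ahead of coaching week 0. It gives no order among them.

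**Endpoint.** The imaging outcomes are labelled week 0 to 16, for example "Change in oxidative phosphorylation (OxPhos) from week 0-16". The MRI/MRS justification in section IV.D gives the purpose as the effect of 16 weeks of supervised training. The MRI/MRS Substudy analysis makes overall change to 16 weeks the primary imaging endpoint and the HIIT-CME comparison secondary. Its list of covariates includes neither scan timing nor coaching arm. Section F calls the muscle substudy exploratory.

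**The concern.** A scan four weeks after the last supervised session does not measure the end of 16 weeks of training. In the interval participants exercise on their own or not at all, and may already have been allocated to coaching or control.

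The protocol expects behaviour to change at this point. It hypothesises that "older PWH randomized to HIIT will maintain self-directed exercise better than those in CME when exercise is no longer supervised". Its preliminary data report that fewer than half of earlier participants exercised at least one day a week 12 weeks after supervision ended.

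Three results are exposed:

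- the overall imaging change, if adaptation is lost before a late scan;
- the HIIT-CME contrast, if loss or maintenance differs by arm;
- the association in Hypothesis 2B between in vivo mitochondrial change and muscle mitochondrial content and oxidative capacity, because scan and biopsy may catch the same person in different training states.

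**Working it through.** **1. Dates.** The inputs are the two windows, week 16 for the second randomisation, and a 12-week (84-day) maintenance phase.

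| Measure | Latest day after last session | Share of 84 days |
|---|---|---|
| MRI/MRS | 28 | 28/84 = 33% |
| Biopsy (requested) | 10 | 10/84 = 12% |

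The limits differ by 28 − 10 = 18 days. The latest permitted scan falls at week 16 + 4 = 20.

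**2. The plan's own power figure.** For PDFF, section F states more than 80% power to detect 9.8% between groups with 12 per group, and 8.7% overall with N = 24. No SD is given, so neither can be reproduced directly. Assume two-sided alpha 0.05, as stated for Aims 1 and 2. With the noncentral t distribution, 80% power needs a standardised difference of 1.197 for 12 versus 12 (noncentrality 1.197 × √(12/2) = 2.93), and 0.597 for a paired test with N = 24 (0.597 × √24 = 2.93). The implied SDs of change are 9.8/1.197 = 8.2 and 8.7/0.597 = 14.6. These disagree, which is a separate matter. If 14.6 were right, power for a 9.8% group difference would be about 35%. The steps below simply start from the stated 80%.

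**3. Dilution (assumed).** The documents give no rate at which adaptation is lost. If a share p of scans is late and each loses a fraction f of the effect, the average effect is multiplied by 1 − p × f, and so is the noncentrality.

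| Average dilution p × f | Power, HIIT vs CME, 12 per group | Power, overall change, N = 24 | Per group to regain 80% (HIIT vs CME) |
|---|---|---|---|
| 10% | 71% | 71% | 15 |
| 20% | 61% | 61% | 19 |
| 30% | 50% | 50% | 24 |
| 50% | 29% | 29% | 45 |

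If half the scans are late and lose 20%, dilution is 0.5 × 0.2 = 10% and power is 71%. If a quarter are late and lose 20%, dilution is 5% and power is 76%.

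**4. Coaching.** With coaching split evenly within each exercise arm, its main effect is the same in both arms and cancels from the HIIT-CME difference. It adds variance. An effect of c SD multiplies the variance by 1 + c²/4:

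- c = 0.25: factor 1.016, power 79%
- c = 0.5: factor 1.063, power 78%
- c = 1.0: factor 1.25, power 71%

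These figures suppose that every scan is exposed to coaching. Balance inside the imaging subset is not guaranteed. With independent allocation and 12 per arm, the difference in coached share has SD √(2 × 0.25/12) = 0.20.

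**The case against.** **Four weeks is an outer limit.** The sentence names week 16 first, and Table 3 schedules the scan with the biopsy ahead of coaching week 0. If sites book to that schedule, few scans are late, and coaching may not start until the scan is done. This stands as far as it goes: the share of late scans is unknown. But no text requires that order. Even if coaching waits, the participant may be 28 days past supervised training.

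**The biopsy limit is only a request.** That is so. The mismatch is between a permitted window and a requested one, and Hypothesis 2B uses only participants with both measures.

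**Coaching cannot confound the exercise contrast.** A reader might infer that it does. The protocol rules this out on average: "participants will be randomized 1:1 (with even allocation of HIIT vs CME) to receive the coaching or control intervention". Bias would need an interaction or chance imbalance in the small imaging subset.

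**Late scans favour HIIT.** A reader might infer this from the maintenance hypothesis, but it is a hypothesis. The figure of fewer than half is at 12 weeks, is not split by arm, and comes from a study of continuous exercise at two intensities, not HIIT. Equal proportional loss in both arms would instead shrink a true HIIT advantage.

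**The substudy is exploratory.** True, and it limits the weight of the point.

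**Conclusion.** The point holds as a gap in the rules for timing. The plan lets a scan up to 28 days after training stand as week-16 data, does not order it against the second randomisation, and neither adjusts for nor examines timing. Late scans can dilute the overall imaging change, can bias the HIIT-CME contrast through arm-dependent loss or maintenance, and can weaken the imaging-biopsy association. Coaching mainly adds noise.

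No size of bias follows from the documents. A reader might take 12.5% as each arm's true PDFF change, let CME lose 10 to 30 percentage points more of it than HIIT, and obtain 0.10 × 12.5 = 1.3 to 0.30 × 12.5 = 3.8 points, or 13% to 38% of 9.8. That is not supported. In section F, 12.5% is a within-group difference detectable with 12 participants, not an expected gain. The extra loss has no source, and every scan would have to be at day 28. The power figures above are likewise illustrations, resting on an assumed dilution and the stated 80%.

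This is a cheap improvement to an exploratory substudy. The 400-m walk primary outcome is unaffected.

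**What to change.** Amend the imaging sentence under Baseline visit #4 in three respects:

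- target the scan within 10 days of the last supervised session, matching the biopsy request;
- state that it precedes disclosure of the second allocation and the first coaching text;
- record days since the last supervised session for scan and biopsy.

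The second item is needed in its own right, because a 10-day window alone does not put the scan before a week-16 randomisation.

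In the MRI/MRS Substudy analysis, keep later scans in the main set. Add a sensitivity analysis restricted to in-window scans, or adjusted for days since the last session. Excluding late scans from the main analysis would cost information, with only about 12 evaluable per arm, and would select on something that happens after randomisation.

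The cost is a short amendment and tighter scanner booking for up to 40 participants. Booking must fit the existing spacing: two days without vigorous activity before imaging, at least 48 hours between the VO2 test and the biopsy, and 48 hours without activity after the biopsy.

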**Intervention:** Participants will complete 16 weeks of supervised CME or HIIT 3 days/week in the University of Colorado-Denver Exercise Research Laboratory, at the Prevention Center at Fred Hutch (University of Washington (UW) site, and at the Center of Exercise Medicine at University of Alabama. Participants will be given the option to complete 16 weeks of exercise at a recreational center if travel to the University of Colorado-Denver, University of Washinton, and University of Alabama at Birmingham is difficult. The recreation center must meet certain requirements (see risk section). Our study staff will visit the site in advance to ensure appropriate equipment is available. Any fees for membership will be covered by the study team (paid directly to the recreation center, not to the participant). Weeks 1-2 will focus on familiarization with the exercises at low intensity. These sessions will still occur at the University of Colorado-Denver center even if a participant choses to exercise at a local recreation center for the remainder of the 16 weeks. The intensity and duration of exercise will be progressed over the first 3-8 weeks to reach the individualized goals. The HIIT and CME interventions will be matched for exercise volume using standard equations for estimating caloric expenditure assuming 5 kcal/L O2 and 50 min/session duration for CME to meet the PA guidelines (Table 4). The total exercise time will differ by 8 minutes, but HIIT includes rest intervals and variety, which prior studies have shown is associated with greater enjoyment and physiologic benefits than CME.

**HIIT.** Following a 5-minute warm-up at 50% HRR (Heart rate reserve), high and moderate-intensity exercise bouts will alternate: Five bouts of 4-minute high-intensity exercise (90% HRR) will alternate with four 3-minute bouts of moderate-intensity exercise (50% HRR). The total exercise time will be 42 minutes.

**CME.** Following a 4 minute warm-up at 50%  $\text{VO}_{2\text{peak}}$ , the participant will walk for 50 continuous minutes at 60% HRR^140.

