**Table 4. Example Aerobic Exercise Prescriptions**

| Participant weight = 78 kg and $\text{VO}_{2\text{peak}}$ = 25.2 ml/kg/min |       |             |      |            |
|--|-------|-------------|------|------------|
|  | % HRR | # Intervals | kcal | Total time |
| CME   | 60    | 1 x 50 min  | 290  | 50 min     |
| HIITa (low)  | 50    | 4 x 3 min   | 288  | 42 min     |
| HIIT (high)   | 90    | 5 x 4 min   |      |            |
| a alternating low/high-intensity, starting with low-intensity   |       |             |      |            |

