All participants will begin with a 2-week supervised, low-intensity exercise acclimation with an experienced research assistant. The initial goal will be to walk on a treadmill for 20-30 continuous minutes at low-intensity (30-40% of maximal aerobic power [ $\text{VO}_{2\text{max}}$ ]) and complete 3 sets of 8 repetitions at low-intensity (40-50% of the one-repetition maximum; 1-RM) 3 or 4 days/week. This will facilitate comfort with study equipment and minimize injury.

At 2 weeks, all participants will complete an additional 14 weeks of moderate- intensity continuous exercise or HIIT in the University of Colorado-Denver Exercise Research Laboratory, at the Prevention Center at Fred Hutch (UW), the Center for Exercise Medicine at University of Alabama, or at a recreational center of their choosing. Weeks 1-2 will focus on familiarization with the exercises at low intensity. The intensity and duration of exercise will be progressed over the first 3-8 weeks to reach the individualized goals. The HIIT and CME interventions will be matched for exercise volume using standard equations for estimating caloric expenditure assuming 5 kcal/L  $\text{O}_2$  and 50 min/session duration for CME to meet the PA guidelines (Table 4). The total exercise time will differ by 8 minutes, but HIIT includes rest intervals and variety, which prior studies have shown is associated with greater enjoyment and physiologic benefits than CME.

**HIIT.** Following a 5-minute warm-up at 50% HRR, high and moderate-intensity exercise bouts will alternate: Five bouts of 4-minute high-intensity exercise (90% HRR) will alternate with four 3-minute bouts of moderate-intensity exercise (50% HRR). The total exercise time will be 42 minutes.

**CME.** Following a 4 minute warm-up at 50%HRR, the participant will walk for 50 continuous minutes at 60% HRR^140.

**Resistance Exercise (For Both HIIT and CME).** The initial goal will be to complete 3 sets of 8-10 repetitions of 3 exercises at low intensity (50% 1-RM) and then progress to moderate intensity (70-80% 1-RM). Exercise intensity will increase every 4 weeks or when participants can complete more than 8 repetitions with proper form at the prescribed weight. The exercises will be leg press, lateral pulldown, and a chest press, all on weight-stack equipment.

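### The HIIT segments the protocol describes add up to 32 minutes (37 with warm-up), not 42, and do not support the stated equal-volume match with CME

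*Combined protocol and SAP*

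**What the plan says.** The overarching hypothesis, in the opening section on hypotheses and aims, is that HIIT will outperform CME, and it adds "that with the same volume of exercise". Section IV.C (Intervention) and section IV.D (Exercise testing and training) both say that the arms are matched on estimated caloric expenditure, using 5 kcal per litre of oxygen and a 50-minute CME session. On duration they say "The total exercise time will differ by 8 minutes".

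Both sections describe the HIIT session in the same way: a 5-minute warm-up at 50% HRR, then five 4-minute bouts at 90% HRR that "will alternate with four 3-minute bouts of moderate-intensity exercise (50% HRR). The total exercise time will be 42 minutes". CME is 50 continuous minutes at 60% HRR after a 4-minute warm-up. Section IV.C sets that warm-up at 50% of VO2peak. Section IV.D sets it in HRR: "Following a 4 minute warm-up at 50%HRR, the participant will walk for 50 continuous minutes".

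Table 4, printed in both sections, works an example for a 78 kg participant with a VO2peak of 25.2 ml/kg/min. CME is 1 x 50 min, 290 kcal, 50 min. HIIT is 4 x 3 min low plus 5 x 4 min high, 288 kcal, 42 min. A footnote to HIIT reads "alternating low/high-intensity, starting with low-intensity".

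**The concern.** The HIIT total cannot be obtained from the segments listed beside it, and both the 8-minute difference and the near-equality of 288 and 290 kcal depend on that total. No cool-down or other HIIT segment is described. The only cool-down in the protocol belongs to strength testing.

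The hypothesis compares interval and intensity at constant volume. If the session actually delivered is the one described, HIIT does less work than CME, and the contrast on 400-m walk time mixes intensity with volume. A null or reversed result would then be hard to interpret, because less work in the HIIT arm could explain it. A HIIT advantage would not be undermined in the same way.

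**Working it through.** **Inputs.** Table 4: weight 78 kg, VO2peak 25.2 ml/kg/min. Section IV.C: 5 kcal/L; HIIT 20 min at 90% and 12 min at 50%, plus a 5-min warm-up at 50%; CME 50 min at 60%, plus a 4-min warm-up at 50%.

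**Time.**
- HIIT bouts: 5 x 4 + 4 x 3 = 32 min. With warm-up: 37 min. Stated: 42 min.
- Gap to CME: 50 - 32 = 18 min with no warm-ups, 54 - 37 = 17 min with both, 50 - 37 = 13 min with only the HIIT warm-up. Stated: 8 min, which is 50 - 42.

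**Reproducing the CME energy figure first.** Three conversions from % HRR to oxygen uptake were tried:
- Fraction of VO2peak: 78 x 25.2 / 1000 x 5 = 9.828 kcal/min at 100%. CME = 50 x 0.60 x 9.828 = 294.8 kcal, 1.7% above the stated 290.
- Gross VO2 reserve, resting uptake assumed at 3.5 ml/kg/min: 50 x (3.5 + 0.60 x 21.7) x 0.39 = 322.1 kcal, 11% above.
- Net VO2 reserve, same assumption: 50 x 0.60 x 21.7 x 0.39 = 253.9 kcal, 12% below.

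(Here 21.7 = 25.2 - 3.5 and 0.39 = 78 x 5 / 1000.) Only the first comes within 3% of Table 4, so it is used below.

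**HIIT as described.**
- Bouts only: (20 x 0.90 + 12 x 0.50) x 9.828 = 24 x 9.828 = 235.9 kcal, 18% below the stated 288.
- With warm-up: 26.5 x 9.828 = 260.4 kcal, 9.6% below 288.

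**HIIT against CME.** CME with its warm-up is (30 + 4 x 0.50) x 9.828 = 314.5 kcal.

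| Segments counted | HIIT kcal | CME kcal | HIIT lower by |
|---|---|---|---|
| Main sets only | 235.9 | 294.8 | 20.0% |
| Both warm-ups | 260.4 | 314.5 | 17.2% |
| HIIT warm-up only | 260.4 | 294.8 | 11.7% |

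The percentages are ratios of weighted minutes (24/30, 26.5/32, 26.5/30), so under this conversion they do not depend on the example participant's weight or VO2peak.

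**What would recover Table 4.** With 20 min at 90%, reaching 288 kcal takes (288 / 9.828 - 18) / 0.50 = 22.6 min at 50%. The text supplies 12 + 5 = 17, so about 5.6 min are missing. Adding 5 min at 50% gives 42 min and (18 + 22 x 0.50) x 9.828 = 285.0 kcal, within 1% of 288. That 42 includes the HIIT warm-up, while CME's 50 excludes its own. Counting the CME warm-up as well, HIIT is 1 - 285.0/314.5 = 9.4% lower. Counting neither warm-up, HIIT is 260.4 against 294.8, or 11.7% lower.

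**The case against.** The strongest reply is that the description is incomplete and the match is sound in intent. Table 4's 42 minutes and 288 kcal agree with each other for 20 minutes at 90% and 22 at 50%, and one undescribed 5-minute segment at 50% restores the total, the energy figure and the 8-minute difference together. That reading is at least as plausible as a true imbalance. A reader might infer that the arms are prescribed unequal volumes, or that sites will deliver different sessions. The documents do not establish either: they state the intent to match, they describe standardised trainer training, session logs and monthly cross-site supervision, and they refer to a manual of procedures that is not available here and may define the full session. What survives is that the written segments do not support the match, and that the completed reading still treats warm-up differently in the two arms.

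It can also be said that Table 4 is only an example and that prescriptions are individualised. But the bout list and the 42-minute total are general text in sections IV.C and IV.D, outside the example.

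Two further stronger readings fail. A shortfall of about 23% can be obtained from gross VO2 reserve, but that conversion misses the plan's own CME figure by 11%. And the footnote on starting low is not impossible with four low and five high bouts: it fits if the 50% HRR warm-up is the opening low stage. The table does not say so, which makes it ambiguous.

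The difference in the CME warm-up unit is real but minor. Under the conversion used here both units give the same energy.

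**Conclusion.** The point holds as a contradiction within the protocol. The described HIIT session is 32 minutes (37 with warm-up), against a stated 42, and the gap to CME is 13 to 18 minutes, against a stated 8. Estimated HIIT energy is 17 to 20% below CME when warm-ups are treated alike, and about 12% below when only the HIIT warm-up is counted. If an omitted 5-minute segment at 50% is supplied, the shortfall is about 9% with both warm-ups counted. No reading confined to the described segments supports the equal-volume statement.

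The minutes follow from the text alone. The energy figures assume that % HRR can be read as % VO2peak, which the plan does not state. It is the only conversion of the three tried that reproduces the CME entry. Whether sessions as delivered differ in volume cannot be determined from these documents.

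**What to change.** The sponsor should reconcile, across sections IV.C and IV.D and both printings of Table 4, the segment list, the 42-minute total, the 8-minute difference, the kcal entries, the starting-bout footnote and the unit of the CME warm-up. The protocol should state the energy equation, including the step from % HRR to oxygen uptake, and which segments count, with warm-up treated the same way in both arms. Table 4 should then be recomputed. Which session is the intended one is for the sponsor to say; no prescription is proposed here.

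If the reconciled sessions are not equal in estimated kcal, the equal-volume phrase in the hypothesis and conclusions should be qualified. In either case, report delivered minutes by arm from the session logs, and estimated kcal where the logs allow. The protocol does not list the log fields, so the kcal summary may not be possible for every session.

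The cost is wording in the protocol and manual, a recalculated table and one descriptive table. The main downside is that the equal-volume claim may have to be softened.
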